6.12.4.1. Leukocytes (WBC) and Platelets

Further analyses will be conducted for total leukocytes, neutrophils, platelets, lymphocytes, monocytes, eosinophils, and basophils. Neutrophils will include both segmented neutrophils and absolute neutrophils (derived by adding segmented neutrophils and band neutrophil). The segmented neutrophils and absolute neutrophils will be summarized using the same categories.

Shift table will be produced showing the number and percentage of patients shifting from baseline to a minimum postbaseline result in each relevant category by treatment groups for study Period 2, Period 3, and Combined Periods 2 and 3, respectively:

- Scheduled visits, unscheduled visits, and repeat measurements will be included.
- Baseline is defined as the minimum result during the defined baseline period or baseline.
- Use the minimum nonmissing postbaseline value within each study period.
- The parameters and categories are:
 - Leukocytes: $\geq 1 \times \text{LLN}$ (Normal), $< \text{LLN}$ to $\geq 3.0 \times 10^9/\text{L}$ (Grade 1), $< 3.0 \times 10^9/\text{L}$ to $\geq 2.0 \times 10^9/\text{L}$ (Grade 2), $< 2.0 \times 10^9/\text{L}$ to $\geq 1.0 \times 10^9/\text{L}$ (Grade 3), and $< 1.0 \times 10^9/\text{L}$ (Grade 4).
 - Neutrophils: $\geq 1 \times \text{LLN}$ (Normal), $< \text{LLN}$ to $\geq 1.5 \times 10^9/\text{L}$ (Grade 1), $< 1.5 \times 10^9/\text{L}$ to $\geq 1.0 \times 10^9/\text{L}$ (Grade 2), $< 1.0 \times 10^9/\text{L}$ to $\geq 0.5 \times 10^9/\text{L}$ (Grade 3), and $< 0.5 \times 10^9/\text{L}$ (Grade 4).
 - Platelets: $\geq 1 \times \text{LLN}$ (Normal), $< \text{LLN}$ to $\geq 75.0 \times 10^9/\text{L}$ (Grade 1), $< 75.0 \times 10^9/\text{L}$ to $\geq 50.0 \times 10^9/\text{L}$ (Grade 2), $< 50.0 \times 10^9/\text{L}$ to $\geq 25.0 \times 10^9/\text{L}$ (Grade 3), and $< 25.0 \times 10^9/\text{L}$ (Grade 4).
 - Lymphocytes: $\geq 1 \times \text{LLN}$ (Normal), $< \text{LLN}$ to $\geq 0.8 \times 10^9/\text{L}$ (Grade 1), $< 0.8 \times 10^9/\text{L}$ to $\geq 0.5 \times 10^9/\text{L}$ (Grade 2), $< 0.5 \times 10^9/\text{L}$ to $\geq 0.2 \times 10^9/\text{L}$ (Grade 3), and $< 0.2 \times 10^9/\text{L}$ (Grade 4).
- The above LLNs are defined as:
 - Leukocytes: $\text{LLN} = 4.0 \times 10^9/\text{L}$
 - Neutrophils: $\text{LLN} = 2.0 \times 10^9/\text{L}$
 - Platelets: $\text{LLN} = 150 \times 10^9/\text{L}$
 - Lymphocytes: $\text{LLN} = 1.1 \times 10^9/\text{L}$
- With additional categories:
 - Decreased; postbaseline category $<$ baseline category
 - Increased; postbaseline category $>$ baseline category
 - Same; postbaseline category = baseline category.

The change from minimum baseline to minimum postbaseline result for each of these leukocytes and platelets will be summarized graphically using a box plot for Periods 2 and 3, respectively.

6.12.4.2. Neutrophil Follow-Up

Neutrophil counts will be followed throughout the study. Patients will continue in Period 4 until their neutrophil counts have recovered.

The neutrophil follow-up analysis will be conducted on the Neutrophil Follow-Up Population defined as patients who have an absolute neutrophil count < 1500 cells/ μL (SI units: $< 1.5 \times 10^9/\text{L}$) at the last scheduled visit or early termination visit before entering Period 4 and less than the patient's baseline absolute neutrophil count (that is, before first injection at Week 0). These patients are monitored during Period 4 until neutrophil recovery.

Neutrophil clinical recovery is defined as an absolute neutrophil count ≥ 1500 cells/ μL (SI units: $\geq 1.5 \times 10^9/\text{L}$) or greater than or equal to a patient's minimum absolute neutrophil count before first study drug injection at Week 0.

If a patient's neutrophil count has not recovered, within 12 weeks after entering the follow-up period (Visit 802), the patient will return for Visit 803 (12 weeks after Visit 802). Additional

visits may be required for appropriate patient management depending upon the degree of neutropenia. If at Visit 802, a patient has met the criteria for neutrophil recovery, the patient's participation in the study will be considered complete unless the investigator deems additional follow-up may be necessary.

The number and percentage of patients achieving neutrophil clinical recovery will be presented by treatment groups and week interval for the Neutrophil Follow-Up Population for Period 4. The number and percentage of patients with an absolute neutrophil cell count that is at least 25%, 50%, 75%, or 100% of the patient's baseline absolute neutrophil count (that is, before first injection at Week 0), irrespective of absolute neutrophil minimum, will be included in the summary.

6.12.5. Vital Signs and Other Physical Findings

Analyses will be conducted on vital signs and physical characteristics including systolic blood pressure (mmHg), diastolic blood pressure (mmHg), pulse (bpm), weight (kg), BMI (kg/m²).

Change from baseline to last observation for vital signs and physical characteristics will be summarized for patients who have both baseline and at least 1 postbaseline result, for Periods 2 and 3, respectively:

- The scheduled visits/measurements will be included. The unscheduled visits and the repeat measurements will be excluded.
- For the Safety Population for Period 2, the comparisons between and among treatment groups will be conducted using an ANCOVA with treatment groups and baseline value in the model.
- Data will be analyzed based on original scale.

For vital signs and physical characteristics, the observed values at each visit (starting at baseline) and change from baseline to each scheduled visit, respectively, will be displayed in box plots for patients who have both a baseline and at least 1 postbaseline result. These box plots will be used to evaluate trends over time and to assess a potential impact of outliers on central tendency summaries.

- The scheduled visits/measurements will be included. The unscheduled visits and the repeat measurements will be excluded.
- The following summary statistics will be included as a table below the box plot: number of patients with a baseline and at least 1 postbaseline result, mean, standard deviation, minimum, Q1, median, Q3, and maximum.
- Data will be summarized based on original scale.

To assess the effect of administration of study drug on vital signs (blood pressures and pulse rate) among patients, at Weeks 0 and 16 vital signs will be measured before the first injection and 1 hour after the injection. The box plots will be produced for predose and postdose vital signs at Weeks 0 and 16 by treatment groups for the safety population.

The number and percentage of patients with treatment-emergent or follow-up emergent high or low vital sign and weight at any time for Periods 2, 3, and 4, respectively, will be summarized. The comparisons between and among treatment groups will be conducted using Fisher's exact test for the Safety Population for Period 2.

Table RHBW.6.9 defines the high and low baseline values as well as the limits that are specified as treatment-emergent and follow-up emergent. Note that weight does not have an abnormal baseline; therefore, the treatment-emergent and follow-up emergent values are determined by change from baseline.

- All postbaseline scheduled, unscheduled, and repeated measurements will be included.
- To assess increases, change from the maximum value during the baseline period or baseline to the maximum value during each study period will be used.
- To assess decreases, change from the minimum value during the baseline period or baseline to the minimum value during each study period will be used.
- For treatment-emergent high and low:
 - A treatment-emergent **high** result is defined as a change from a value less than or equal to the high limit at baseline to a value greater than the high limit at any time that meets the specified change criteria during the treatment period.
 - A treatment-emergent **low** result is defined as a change from a value greater than or equal to the low limit at baseline to a value less than the low limit at any time that meets the specified change criteria during the treatment period.
- For follow-up emergent high and low:
 - A follow-up emergent **high** result is defined as a change from a value less than or equal to the high limit at baseline to a value greater than the high limit at any time that meets the specified change criteria during the follow-up period.
 - A follow-up emergent **low** result is defined as a change from a value greater than or equal to the low limit at baseline to a value less than the low limit at any time that meets the specified change criteria during the follow-up period.

Table RHBW.6.9. Categorical Criteria for Abnormal Treatment-Emergent Blood Pressures and Pulse Measurement, and Categorical Criteria for Weight Changes for Adults

Parameter	Low	High
Systolic BP (mm Hg) ^a (supine or sitting – forearm at heart level)	≤90 and decrease from baseline ≥20	≥140 and increase from baseline ≥20
Diastolic BP (mm Hg) ^a (supine or sitting – forearm at heart level)	≤50 and decrease from baseline ≥10	≥90 and increase from baseline ≥10
Pulse (bpm) ^a (supine or sitting)	<50 and decrease from baseline ≥15	>100 and increase from baseline ≥15
Weight (kg)	(Loss) decrease from baseline ≥7%	(Gain) increase from baseline ≥7%

Abbreviations: BP = blood pressure; bpm = beats per minute; kg = kilogram; mm Hg = millimeters of mercury.

^a Baseline abnormal values are defined by the value presented.

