## 4. Study Design

### 4.1. Overview of Study Design

Study IIF-MC-RHBW (RHBW) is a Phase 3, multicenter, randomized, double-blind, placebo-controlled, parallel-group, outpatient study examining the efficacy and safety of 2 ixekizumab treatment regimens (80 mg Q2W and 80 mg Q4W SC), as compared to placebo SC in patients with active rad-axSpA who are TNF inhibitor-experienced, during a double-blind, 16-week treatment period (Period 2). Starting doses of 80 mg and 160 mg (at Week 0) will be evaluated for each ixekizumab regimen.

Study RHBW will also evaluate long-term efficacy and safety of ixekizumab during the Extended Treatment Period (Period 3) for a total treatment duration of 1 year (52 weeks). Patients that complete Study RHBW may be eligible to enroll into a long-term study (Study IIF-MC-RHBY [RHBY]) for up to 2 additional years. Patients that do not enroll into Study RHBY will complete the Post-Treatment Follow-Up Period (Period 4) in Study RHBW.

[Figure RHBW.1](#) illustrates the study design; all treatment groups and administration of the investigational product are described in [Section 6.1](#); and the Study Drug Administration Log is described in [Section 6.2.1](#).

All procedures to be conducted during the study, including timing of all procedures, are indicated in the Schedule of Activities ([Appendix 2](#)). Selected study procedures are to be performed prior to administration of the investigational product, as applicable.

For each patient, x-rays will be collected according to [Section 8.1.2.20.1](#) and the Schedule of Activities ([Appendix 2](#)). [Appendix 3](#) lists the specific laboratory tests that will be performed for this study.

[figure not shown]
Patients discontinuing from study treatment who have received at least 1 dose of investigational product will continue to the early termination visit (ETV) prior to proceeding to the Post-Treatment Follow-Up Period. For the management of patient safety, all patients are to be monitored through the Post-Treatment Follow-Up Period at least as frequently as indicated in the Schedule of Activities ([Appendix 2](#)).

In addition to procedures specified in the protocol, a subset of patients (approximately 150) will participate in an MRI addendum. (Sites will be selected by the sponsor, and all patients at those sites will be required to participate in the addendum, as long as they satisfy MRI inclusion criteria.)

Excluded and concomitant medications are detailed in [Section 6.8](#).

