6.1.2. General Considerations for Analyses during the Extended Treatment Period (Period 3)

Unless otherwise specified, Period 3 starts at the first injection of study treatment at Week 16 (Visit 8) and ends on the date of Week 52 (Visit 15) or the ETV (between Weeks 16 and 52).

For the efficacy and health outcomes analyses, baseline is defined as the last available value before the first injection in Period 2 and, in most cases, will be the value recorded at Week 0 (Visit 2).

Unless otherwise specified, for the safety analyses during Period 3, baseline is defined as the last available value before first injection of ixekizumab in Period 3. In most cases, this will be the measure recorded at Week 16 (Visit 8). For treatment-emergent adverse events (TEAEs), baseline is considered as those events that are ongoing before the first injection of the study treatment at Week 16.

The number and percentage of patients having a categorical efficacy response (for example, ASAS40) will be summarized by treatment group for all scheduled visits (nonresponder imputation [NRI]), including Week 52 (Visit 15) during Period 3.

In addition, the number and percentage of patients achieving response on ASAS20 for those patients who did not achieve it at Week 16, and the number and percentage of patients maintaining response for those who achieved response at Week 16 will be summarized by treatment group for all scheduled visits (NRI), including Week 52 (Visit 15) during Period 3. Similar summary will be provided for ASAS40.

Each continuous efficacy and health outcomes score and change from baseline (or percent improvement) will be summarized by treatment group at all scheduled visits, including Week 52 (Visit 15) using descriptive statistics (n, mean, SD, median, minimum, and maximum). Missing data will be imputed using mBOCF method (Section 6.3.2).

The categorical safety measures will be summarized with incidence rates. The mean change of the continuous safety measures will be summarized at all scheduled visits.

6.1.3. General Considerations for Analyses during Combined Blinded Treatment Dosing Period and Extended Treatment Period (Combined Periods 2 and 3)

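### SAP 6.12.5 specifies no Week 0-52 flag or last-observation summary for vital signs and weight, so change that builds across Week 16 on ixekizumab can go uncounted

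*SAP*

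**What the plan says.** Protocol 4.1 sets the aim: "Study RHBW will also evaluate long-term efficacy and safety of ixekizumab during the Extended Treatment Period". The rules that matter here are in the SAP.

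- **Periods.** SAP 6.12.5 counts treatment-emergent "high or low vital sign and weight at any time for Periods 2, 3, and 4, respectively". Change to last observation is for patients with a baseline and "at least 1 postbaseline result, for Periods 2 and 3, respectively". Neither analysis names Combined Periods 2 and 3.
- **Baseline.** SAP 6.1.2 states that "for the safety analyses during Period 3, baseline is defined as the last available value before first injection of ixekizumab in Period 3", and adds that this is usually the Week 16 (Visit 8) measure.
- **Change rule.** For increases, "change from the maximum value during the baseline period or baseline to the maximum value during each study period will be used". Decreases mirror this with minimum values.
- **Thresholds (Table RHBW.6.9).** High systolic pressure is "≥140 and increase from baseline ≥20" mm Hg. High diastolic pressure needs 90 or more and a rise of at least 10. High pulse needs more than 100 and a rise of at least 15. Weight gain or loss needs at least 7%. For blood pressure and pulse, the baseline must also not already be abnormal.
- **Combined period elsewhere.** SAP 6.1.3 promises an unlisted selection of safety analyses over Combined Periods 2 and 3 with a Week 0 baseline, for patients randomized to ixekizumab at Week 0. It also promises further categorical analyses over all ixekizumab exposure. SAP 6.12 includes vital signs in its list of safety data and says in general terms that safety data will be summarized for the combined period. Table RHBW.6.1 does likewise.

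**The concern.** For patients who switch from placebo, Week 16 is the right baseline because it is their last value before ixekizumab. For patients on ixekizumab from Week 0 it is an on-drug value. The Period 3 flag therefore measures further change after 16 weeks of treatment, not change from before treatment.

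The flags need a minimum change within a period, so splitting the year at Week 16 opens two gaps. A gradual change can fall short of the threshold in each part yet exceed it over the year. For blood pressure and pulse, a rise too small to flag in Period 2 can still make the Week 16 value abnormal, and the patient is then not eligible for a high flag in Period 3.

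The patients concerned are the only ones with up to 52 weeks of ixekizumab, in a trial that says it evaluates long-term safety. Other sections do provide for them: 6.12.4.1 names the combined period for leukocyte and platelet shifts, and Table RHBW.6.10 uses Week 0 as the immunogenicity baseline for patients on ixekizumab throughout and Week 16 only for the switchers.

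**Working it through.** The plan gives no figure to reproduce here. The check applies the Table RHBW.6.9 rules to Week 0 to 16, Week 16 to 52 and Week 0 to 52.

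**Worked patients.** The values are invented. Each is taken to be the highest reading in its period, and the Week 0 value the highest pre-treatment reading.

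| Measure | Week 0 | Week 16 | Week 52 | Period 2 change | Period 3 change | Week 0-52 change |
|---|---|---|---|---|---|---|
| Weight, kg | 80 | 85 | 90.5 | +6.3% | +6.5% | +13.1% |
| Systolic, mm Hg | 120 | 132 | 150 | +12 | +18 | +30 |
| Diastolic, mm Hg | 78 | 86 | 95 | +8 | +9 | +17 |
| Systolic, mm Hg | 125 | 142 | 170 | +17 | +28 | +45 |

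Weight: 85/80 = 1.0625, 90.5/85 = 1.0647, 90.5/80 = 1.131.

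None of the four is flagged in Period 2 or Period 3. All four meet the criteria against Week 0. In the first three, the change is below threshold in each period. In the fourth, the Period 3 rise of 28 is large enough, but the Week 16 baseline of 142 is already above the limit of 140.

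**Limit for weight.** With just under 7% in each period:

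- gain: 1.07 × 1.07 − 1 = 0.1449, so up to just under 14.5%;
- loss: 1 − 0.93 × 0.93 = 0.1351, so up to just over 13.5%.

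**Possible size, under assumptions only.** The documents give no standard deviations or drift rates, so these simulated figures are not predictions. About 300 × 2/3 = 200 patients are randomized to ixekizumab.

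- *Weight.* Assumptions: linear change, annual mean 0 to 4%, between-patient SD 4% or 6%, visit noise 1%, readings at Weeks 0, 16, 24 and 52. Of patients who gain at least 7% from Week 0, 50% to 78% have no Period 2 or Period 3 flag. That is about 8 to 32 of 200.
- *Systolic pressure.* Assumptions: mean 126, between-patient SD 12, visit SD 8, annual drift 0 to 10 mm Hg, readings at every scheduled visit. Of patients flagged over Weeks 0-52, 25% to 37% are missed by both period flags. That is about 2 to 11 of 200.

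In the systolic simulation, the Period 3 flag rate (8.1% to 18.0%) is higher than the Week 0-52 rate (4.6% to 14.7%). One reason is that the Period 3 baseline is a single Week 16 reading, while the pre-treatment baseline is the larger of two. For blood pressure, then, the period tables pick out different patients and need not give a lower total.

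**Data.** Protocol Appendix 2 has blood pressure and pulse at every visit, and weight on the eCRF at Visits 2, 8, 10, 15 and/or early termination. A Week 0-52 comparison is possible.

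**The case against.** A reader might infer that vital signs and weight are never assessed over Weeks 0-52. The documents do not support that:

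- SAP 6.1.3, 6.12 and Table RHBW.6.1 provide for combined-period safety summaries, and 6.1.3 defines a Week 0 baseline for measured values as well as for adverse events.
- The 6.12.5 box plots show observed values at each visit from baseline, with summary statistics and no stated period limit. Observed values do not depend on the choice of baseline, so group drift stays visible.
- Protocol 8.4.10.3 compares each patient's blood pressure with Week 0. Clinically significant vital-sign findings that lead to a diagnosis become adverse events, which are summarized over the combined period.

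A reader might also infer that all of the roughly 200 patients randomized to ixekizumab are affected. They are not. A flag is lost only when the change straddles Week 16 below threshold, or when a smaller Period 2 rise leaves an abnormal Week 16 value. Frequent readings and the use of period maxima give blood pressure more chances to be flagged than a three-reading example suggests.

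It is also fair to say that other safety topics lack a combined-period analysis (hepatic elevation categories and depression events in Table RHBW.6.8), and that Weeks 16 to 52 have no control group, so a one-year count cannot isolate a drug effect.

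All of this stands and limits the point. It does not remove it. The section that governs these tables names its periods and leaves the combined one out. An unlisted selection does not tell the programmer to produce the missing table, and box plots do not count patients who cross a threshold.

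**Conclusion.** The point holds as a gap in specification with a real consequence. SAP 6.12.5 defines no Week 0-52 flag and no Week 0-52 last-observation summary for vital signs and weight, and the general sections do not say that these are among the combined-period analyses. If 6.12.5 is followed as written, a patient on ixekizumab throughout can gain up to just under 14.5% in weight, or have a systolic rise of 30 to 45 mm Hg as in the examples, and appear in no treatment-emergent count.

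This assumes that the Period 3 baseline is the Week 16 value, as 6.1.2 says it usually is. How many patients would be affected cannot be known from the documents; the simulated ranges rest wholly on assumed values. No efficacy result is touched, and the placebo-controlled safety comparison in Period 2 already uses the pre-treatment baseline. The change should be made, but the trial's main conclusions do not depend on it.

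**What to change.** In SAP 6.12.5, add Combined Periods 2 and 3 for the Safety Population initially randomized to ixekizumab, using the Week 0 baseline already defined in 6.1.3, for:

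- (a) change from baseline to last observation in vital signs and weight;
- (b) treatment-emergent high or low blood pressure and pulse, and weight change of at least 7% in either direction.

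Label both as descriptive, with no control after Week 16. Keep the Period 3 tables with the Week 16 baseline for the patients who switch from placebo. The same combined-period summary of continuous laboratory change in 6.12.4 is optional.

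The cost is a short text change and a few more tables, since the population, baseline rule and data already exist. Reported abnormality counts may be somewhat higher, most plainly for weight.

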6.12.6. Quick Inventory of Depressive Symptomatology–Self Report 16 items (QIDS-SR16)

The QIDS-SR16 is a self-administered 16-item instrument intended to assess the existence and severity of symptoms of depression as listed in the American Psychiatric Association’s (APA’s) *Diagnostic and Statistical Manual of Mental Disorders, 4th Edition (DSM-IV)* (APA 1994). The QIDS-SR16 scale is used to assess the potential impact of treatment on new onset or changes in depression, thoughts of death, and/or suicidal ideation severity. A patient is asked to consider each statement as it relates to the way they have felt for the past 7 days. There is a 4-point scale for each item ranging from 0 to 3. The 16 items corresponding to 9 depression domains are summed to give a single score ranging from 0 to 27, with higher scores denoting greater symptom severity. Additional information and the QIDS-SR16 questions may be found at the University of Pittsburgh IDS/QIDS [WWW] resource page (<http://www.ids-qids.org>).

The 9 domains assessed by the instrument are defined as:

- 1) **Sleep disturbance** (initial, middle, and late insomnia or hypersomnia): the highest score recorded for the 4 sleep items: #1 (falling asleep), #2 (sleep during the night), #3 (waking up too early) and #4 (sleeping too much). Domain is missing if all items are missing.
- 2) **Sad mood**: Item #5 (feeling sad). Domain is missing if the item is missing.
- 3) **Decrease/increase in appetite/weight**: the highest score recorded for the appetite/weight items: #6 (decreased appetite), #7 (increased appetite), #8 (decreased weight within the last 2 weeks), and #9 (increased weight within the last 2 weeks). Domain is missing if all items are missing or not applicable.
- 4) **Concentration**: Item #10 (concentration/decision making). Domain is missing if the item is missing.
- 5) **Self-criticism**: Item #11 (view of myself). Domain is missing if the item is missing.

- 6) **Suicidal ideation:** Item #12 (thoughts of death or suicide). Domain is missing if the item is missing.
- 7) **Interest:** Item #13 (general interest). Domain is missing if the item is missing.
- 8) **Energy/fatigue:** Item #14 (energy level). Domain is missing if the item is missing.
- 9) **Psychomotor agitation/retardation:** The highest score recorded for the 2 psychomotor items: #15 (feeling slowed down) and #16 (feeling restless). Domain is missing if all items are missing.

The QIDS-SR16 total score is the sum of the above domain scores. The total score will be missing if any domain score is missing.

The QIDS-SR16 total scores are categorized as follows:

- None (no depression): 0 – 5
- Mild: 6 – 10
- Moderate: 11 – 15
- Severe: 16 – 20
- Very severe: 21 – 27

The following summaries will be produced for QIDS-SR16 total score category by treatment groups for Safety Population during Periods 2 and 3:

- The number and percentage of patients falling into each QIDS-SR16 total score category at each scheduled visit.
- Shift from maximum baseline to each postbaseline visit in QIDS-SR16 total score category.
- The number and percentage of patients falling into the following categories based upon the maximum postbaseline QIDS-SR16 total score:
 - Improved; maximum postbaseline category < maximum baseline category
 - Worsened; maximum postbaseline category > maximum baseline category
 - Same; maximum postbaseline category = maximum baseline category

In addition, the number and percentage of patients falling into the following groups based upon the maximum postbaseline QIDS-SR16 item 12 (Thoughts of Death or Suicide) score will be summarized by treatment groups for the Safety Population during the Period 2 and Extended Treatment Period Population for Period 3:

- Improved: maximum postbaseline QIDS-SR16 item 12 score < maximum baseline item 12 score
- Worsened; maximum postbaseline QIDS-SR16 item 12 score > maximum baseline item 12 score

- Same; maximum postbaseline QIDS-SR16 item 12 score = maximum baseline item 12 score

